#### **Protocol Template**

Sponsor: Menarini Pharmaceutical Protocol Version\_1 of 16/07/2020
Study Code: MEIN/19/ZoNe-HYP/001

Hematology	Serum Chemistry
Red blood cell	ALT
White blood cell	Albumin
Hemoglobin	Alkaline phosphatase
Hematocrit	AST
Platelets	Total protein
Neutrophils	Direct bilirubin
Lymphocytes	Total bilirubin
Monocytes	Creatinine
Eosinophils	Blood urea nitrogen
•	Creatine kinase
Basophils	GGT
Neutrophils absolute, Lymphocytes	Triglycerides
absolute, Monocytes absolute,	Cholesterol
Eosinophils absolute, Basophils absolute	High- and low-density lipoprotein
	Chloride
	Blood glucose
	Serum potassium

Note: Patients who will be reported with an abnormal renal function (creatinine clearance <30 mL/min) and/or abnormal liver enzyme parameters (alanine aminotransferase [ALT] or aspartate aminotransferase [AST] level of >2.5 × upper limit of normal [ULN] or bilirubin level >1.5 × ULN) will be withdrawn from treatment and study

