### 14.5.6 Subgroup Analysis

Subgroup analysis will be conducted using ITT and PP population based on the following parameters.

- Country/Site
- Age (<40 years and ≥40 years)

- Gender (Male, Female, Other)
- Presence of diabetes (patients with or without diabetes)
- Presence of hypercholesterolemia (patients with or without hypercholesterolemia)
- Screening therapy (ACE-i, Beta blocker)
- Run-in period therapy (Monotherapies of ZOF 30 mg or NEB 5 mg)

Identification Number: FORM-000050125

Previous Doc Number: CTWI10A

Version Number: 1.0, CURRENT

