#### 2.3. EXPLORATORY OBJECTIVES

The exploratory objectives are,

Document: \\ieedc-vnasc01\BIOSdata\Menarini\NebZof\KZA41200\Biostatistics\Documentation\SAP

Author: [name] Version Number: Final V1.0

Version Date: [14Dec2021]

Template No.: CS\_TP\_BS016 Revision 6 Reference: CS\_WI\_BS005

Page 12 of 37

- To assess the antihypertensive efficacy at different time points in patients who
  - 1. received NEB or ZOF monotherapies before the run-in period,
  - 2. received any other ACE-i or BB monotherapies before the run-in period
- To assess the antihypertensive effect on patients, based on their hypertension grade, presence or absence of hypercholesterolemia, presence or absence of diabetes at Visit 2 and Visit 3

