### 7.5. EXAMINATION OF SUBGROUPS

Subgroup analyses will be conducted as stated in the exploratory analysis sections. It should be noted that the study was not designed to detect treatment differences with high statistical power within subgroups.

The following subgroups will be assessed and described within the exploratory analysis sections on ITT and PP populations.

- Country/Site
- Age (<40 years and  $\ge40$  years)
- Gender (Male, Female, Other)
- Hypertension grade at screening (grade 1 and grade 2)
- Presence of diabetes (patients with or without diabetes)
- Presence of hypercholesterolemia (patients with or without hypercholesterolemia)
- Screening therapy (ACE-i, Beta blocker)
- Run-in period therapy (Monotherapies of ZOF 30 mg or NEB 5 mg)

Hypertension grade at screening is derived as follows;

- Grade  $1 140 \le SBP \le 160$  or  $90 \le DBP \le 100$
- Grade  $2 160 \le SBP \le 180$  or  $100 \le DBP \le 110$

Patients with presence of diabetes and hypercholesterolemia will be identified from the medical history data using the preferred terms. Presence of diabetes can be identified with the preferred terms "Diabetes mellitus" Or "Type 2 diabetes mellitus" and hypercholesterolemia with "Dyslipidaemia" or "Hypercholesterolaemia" or "Hyperlipidaemia". Patients under ACE-i and beta blocker can be identified from the concomitant medication data with anatomical therapeutic chemical (ATC) class "Ace inhibitors, plain" and "Beta blocking agents, selective" respectively.

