### 11. MEDICAL HISTORY

Medical History information will be presented for the ENR.

- Medical History data captured on eCRF will be coded using Medical Dictionary for Regulatory Activities (MedDRA, Version 23.1 or latest) dictionary
  - Medical History conditions are defined as those conditions which stop prior to or at Screening.
  - Presented by SOC and PT.

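### The preferred terms in SAP 7.5 do not match the subgroup labels: type 1 and other unlisted diabetes terms count as no diabetes, and two non-specific lipid terms count as hypercholesterolaemia

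*SAP*

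**What the plan says.** Protocol 14.5.6 lists presence of diabetes and, in parallel wording, "Presence of hypercholesterolemia (patients with or without hypercholesterolemia") among the subgroups. It defines neither condition and names no data source. SAP 2.3 makes the effect by "presence or absence of hypercholesterolemia, presence or absence of diabetes at Visit 2 and Visit 3" part of an exploratory objective.

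SAP 7.5 turns the labels into a rule. It states: "Patients with presence of diabetes and hypercholesterolemia will be identified from the medical history data using the preferred terms". It then identifies diabetes with "the preferred terms 'Diabetes mellitus' Or 'Type 2 diabetes mellitus' and hypercholesterolemia with 'Dyslipidaemia' or 'Hypercholesterolaemia' or 'Hyperlipidaemia". No further terms and no other method of identification are given for these two subgroups.

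The planned output is in SAP 16.3.2: the number and percentage of patients at the blood-pressure goal at Visits 2 and 3 in each subgroup of SAP 7.5. No test or estimate of the difference between subgroups is planned.

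**The concern.** The labels and the rule describe different groups of patients.

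- **Diabetes.** The label covers any diabetes. The rule has the general term and the type 2 term but none for type 1. A type 1 patient counts as diabetic if the site's entry is coded vaguely and as not diabetic if it is coded precisely. That is not a coherent decision to study type 2 only.
- **Lipids.** The label is hypercholesterolaemia. Two of the three terms cover lipid disorders in general, so a patient with, say, only raised triglycerides could sit in the hypercholesterolaemia row.

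At stake is the meaning of two pairs of rows in an exploratory table. Readers will set the percentages of each pair side by side, because that comparison is what the exploratory objective is about.

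**Working it through.** The plan states no size, goal rate or difference for these subgroups, so there is no figure to reproduce. The check has three parts.

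**1. Can the misplaced patients exist in this trial?**
Protocol 8.1.1 admits adults from 18 to under 65 years. Protocol 8.1.2 does not name type 1 diabetes. Its exclusion 2 removes serious disorders, endocrine or metabolic ones included, that in the investigator's opinion may limit evaluation. That may reduce the number of type 1 patients but does not rule them out. Nothing in the criteria removes patients with a lipid disorder other than raised cholesterol.

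**2. How far could a difference between rows shrink, if misplacement is unrelated to response?**
Observed difference = true difference × (PPV + NPV − 1). PPV is the share of the 'with' row that truly has the condition. NPV is the share of the 'without' row that truly does not. Let p be the prevalence. Every p, Se and Sp below is an assumption. Only the 216 patients come from the documents (Protocol 14.2), and that number is used for scale.

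*Diabetes terms missing* (specificity 1, sensitivity Se): factor = (1 − p) / [(1 − p) + p(1 − Se)]

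- p = 0.10, Se = 0.98: 0.90 / (0.90 + 0.002) = 0.998
- p = 0.20, Se = 0.95: 0.80 / (0.80 + 0.010) = 0.988. Here 0.20 × 216 = 43 patients have diabetes and 0.05 × 43 ≈ 2 are moved.
- p = 0.30, Se = 0.80: 0.70 / (0.70 + 0.060) = 0.921

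*Lipid terms too broad* (sensitivity 1, specificity Sp): factor = p / [p + (1 − p)(1 − Sp)]

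- p = 0.50, Sp = 0.98: 0.50 / (0.50 + 0.010) = 0.980
- p = 0.30, Sp = 0.90: 0.30 / (0.30 + 0.070) = 0.811
- p = 0.20, Sp = 0.80: 0.20 / (0.20 + 0.160) = 0.556

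Over these ranges the loss is about 0.2% to 8% for diabetes and 2% to 44% for lipids.

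**3. Is shrinkage assured?**
No. Assume diabetes prevalence 20%, a type 1 share of 10% of diabetes, and Visit 3 goal rates of 40% without diabetes and 25% in type 2. The omitted type 1 patients are 0.20 × 0.10 = 2% of all patients and join the 80% without diabetes.

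- Type 1 goal rate 25%. True difference: 40 − 25 = 15.0 points. Observed: (0.80 × 40 + 0.02 × 25) / 0.82 − 25 = 39.6 − 25 = 14.6 points. It shrinks.
- Type 1 goal rate 40%. True difference: 40 − (0.1 × 40 + 0.9 × 25) = 13.5 points. Observed: 40 − 25 = 15.0 points. It grows.

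SAP 3.3 notes that the goal rate at Visit 2 is always zero under the entry rule for the combination. Any difference between rows can therefore arise only at Visit 3.

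**The case against.** The strongest reply is that little depends on these flags. The table is descriptive, no contrast between subgroups is planned, and SAP 7.5 itself disclaims power within subgroups. This stands, and it keeps the point minor. It does not excuse a row whose label differs from its content.

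The SAP also says patients *can* be identified by these terms, so the list might not be meant as exhaustive. But the preceding sentence says they *will* be identified by preferred terms, and no other route is offered. A programmer would code these five terms.

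A further reply is that another fault in SAP 7.5 is larger. The flags are drawn from medical history data, and SAP 11 says: "Medical History conditions are defined as those conditions which stop prior to or at Screening". SAP 12 places ongoing conditions under concurrent diseases, which SAP 7.5 does not name as a source. Suppose, as an assumption, that only 5% to 25% of 43 diabetic patients had a condition that stopped by Screening. The diabetes row would then hold about 2 to 11 patients (0.05 × 43 to 0.25 × 43), whatever the list. That is a fair observation, but correcting the source leaves the same five terms in place, so both repairs are needed.

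Three stronger readings are tempting, and the documents do not support them:

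- *The SAP changes the protocol without listing it in SAP 3.3.* The protocol defines neither condition, so SAP 7.5 puts an undefined label into operation and does not alter a definition.
- *Every dyslipidaemia is counted.* Only three named terms are. A lipid disorder coded to another term is not counted.
- *The subgroups should be rebuilt from Visit 1 laboratory values or drug records, because these are collected.* Reported diagnoses are a legitimate basis for a descriptive subgroup. A lipid-lowering drug alone does not show raised cholesterol, one value above a limit is not a diagnosis, and Protocol 10.2.3 states no fasting requirement.

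**Conclusion.** The point holds as a mismatch between rule and label. Patients coded to type 1 or another unlisted diabetes term would be counted as not diabetic. Patients coded to the two general lipid terms would be counted as hypercholesterolaemic.

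The size cannot be derived from the documents, and the factors above only illustrate assumed ranges. On those ranges the effect is probably small for diabetes and could be more visible for lipids. A reader might infer that the differences between rows must shrink. That requires misplacement unrelated to response, which the documents do not establish, and the example above shows a difference growing.

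The primary analysis of diastolic pressure does not use these flags and is not affected. Severity is minor. One thing rests outside the documents: they do not reproduce the coding dictionary, so its full set of diabetes terms must be read from the dictionary itself.

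**What to change.** Amend SAP 7.5 before database lock and without reference to blood pressure results:

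1. Replace the two diabetes terms with all diabetes mellitus preferred terms, of any type, in the MedDRA version used for the study.
2. For lipids, either rename the subgroup 'dyslipidaemia/hyperlipidaemia including hypercholesterolaemia', or keep the label and show the cholesterol-specific term as a separate row.
3. Apply the lists to whichever form or forms hold the patients' conditions.

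The cost is a few lines of SAP text, a term list and a small programming change on data already coded. No new data are needed, and nothing changes in the conduct of the trial or the primary analysis. The separate cholesterol row may be small. Renaming avoids that, at the price of a subgroup broader than the one named in the objective.

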4. STUDY SCHEME

BP: Blood pressure, NEB: Nebivolol, ZOF: Zofenopril calcium, ACE-i: Angiotensin converting enzyme-inhibitors, BB: Beta blockers

- Patients meeting the eligibility criteria at Screening (Visit 1), will enter the run-in period on the same day
- Patients who were on ZOF or NEB treatment at Screening, will continue to receive the same drugs; the
  patients on any other ACE-i will start ZOF and patients who were on any other BB will start NEB from the
  same day
- Only patients with uncontrolled BP (sitting SBP/DBP >130/80 mmHg) and whose adherence to the treatment ranges from 80% to 120%, will enter the assessment period to receive the extemporaneous combination of NEB and ZOF; while the patients with controlled sitting BP (SBP/DBP ≤130/80 mmHg) and/or the patients who do not tolerate the treatment and patients with uncontrolled BP whose adherence to the therapy do not range from 80% to 120%, will be withdrawn from the study.

Identification Number:
FORM-000050125
Previous Doc Number:
CTWI10A
Version Number:

1.0, CURRENT

Sponsor: Menarini International Operations Luxembourg
Study Code: MEIN/19/ZoNe-HYP/001
Protocol Version\_1 of 16/07/2020

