#### 7. STUDY DESIGN

This is a phase IV, open-label, multicenter, multinational, interventional study to assess the effectiveness and safety of the extemporaneous combination of NEB and ZOF in grade 1 to 2 hypertensive patients versus each monotherapy (NEB or ZOF).

The study will be conducted in approximately 15 sites in the European Union countries. The total study duration is 12 weeks including a run-in period of 4 weeks and an assessment period of 8 weeks.

At Visit 1, after providing informed consent, the eligible grade 1-2 hypertensive patients (with blood pressure [BP] ranging from ≥140/90 mmHg to ≤179/109 mmHg), who were on treatment since at least 1 month, with any ACE-i or BB including ZOF 30 mg and NEB 5 mg will be screened for the eligibility criteria including BP. On the same day, the eligible patients will enter the run-in period of 4 weeks (Week -4 to Week 0). Efforts will be made to achieve 1:1 ratio in the enrolment of patients receiving any ACE-i or BB. The eligibility for grade 1-2 hypertension will be based upon the European Society of Cardiology/European Society of Hypertension (ESC/ESH) guidelines 2018, and the BP criteria is defined as mean sitting SBP ≥140 mmHg and ≤179 mmHg and/or mean sitting DBP ≥90 mmHg and ≤109 mmHg.

During the run-in period of 4 weeks (Week -4 to Week 0):

 Patients on ZOF 30 mg or NEB 5 mg will continue the same therapy. Patients on any other ACE-i will be assigned to monotherapy with ZOF 30 mg and the patients on any other BB will be assigned to monotherapy with NEB 5 mg, respectively.

Patients with controlled BP (sitting SBP/DBP ≤130/80 mmHg), at Week 0 (Visit 2), patients with uncontrolled BP (sitting SBP/DBP >130/80 mmHg) whose adherence to the treatment is not included from 80% to 120% or patients who cannot tolerate one of the monotherapies will not proceed further into the study.

Identification Number: FORM-000050125

Previous Doc Number:
CTWI10A

Version Number: 1.0, CURRENT

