#### 9.6 Non-Permitted Medications

The patients will not be permitted to use any of the following medications from Screening till the end of treatment. Blood pressure modifying drugs including alpha receptor blockers and agonists, beta receptor blockers and agonists, calcium antagonists, ACE-i, diuretics, centrally acting antihypertensives (eg, clonidine, methyldopa, guanfacine), reserpine, moxonidine, chronic nitrate treatment (eg, isosorbide dinitrate or isosorbide mononitrate) and angiotensin II antagonists are not permitted, even if used for other indications.

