#### 13. MEDICATIONS

Medications will be presented for the SAF and coded using WHO Drug dictionary Version 01SEP2020 or latest. See Appendix 2 for handling of partial dates for medications, in the case where it is not possible to define a medication as prior, concomitant, the medication will be classified by the worst case, i.e. concomitant.

Frequency tabulations will be presented for prior and concomitant medications by primary therapeutic subgroup (3rd

Document: \\ieedc-vnasc01\BIOSdata\Menarini\NebZof\KZA41200\Biostatistics\Documentation\SAP

Author: [name] Version Number: Final V1.0

Version Date: [14Dec2021]

Template No.: CS\_TP\_BS016 Revision 6 Reference: CS\_WI\_BS005

Page 24 of 37

level ATC code) and preferred name.

- 'Prior' medications are medications which started and stopped prior to the first dose of study medication.
- 'Concomitant' medications are medications which:
  - o started prior to, on or after the first dose of study medication,
  - AND ended on or after the date of first dose of study medication or were ongoing at the end of the study.

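### SAP 7.5 finds beta-blocker patients only through the selective ATC class and names an ambiguous data source, so some patients would have no screening-therapy class (low severity, descriptive output only)

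*SAP*

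**What the plan says.** SAP 7.5 lists two neighbouring subgroups: "Screening therapy (ACE-i, Beta blocker") and "Run-in period therapy (Monotherapies of ZOF 30 mg or NEB 5 mg"). For the first it gives one derivation: "Patients under ACE-i and beta blocker can be identified from the concomitant medication data with anatomical therapeutic chemical (ATC) class". For beta blockers the class named is "Beta blocking agents, selective"; for ACE inhibitors it is the plain ACE-inhibitor class.

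SAP 13 sorts medications by date: "Prior' medications are medications which started and stopped prior to the first dose of study medication". Concomitant ones end on or after that dose, or are still ongoing at the end of the study. SAP 6.1 sets the reference date at the first combination dose, at Visit 2.

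Protocol 8.1.1 admits patients on ACE-inhibitor or beta-blocker monotherapy without limiting the type of beta blocker. Protocol 7 fixes what follows at Visit 1: "Patients on any other ACE-i will be assigned to monotherapy with ZOF 30 mg and the patients on any other BB will be assigned" to NEB 5 mg. Patients on ZOF 30 mg or NEB 5 mg stay on it. Protocol 9.6 lists BP-modifying drugs, beta blockers and ACE inhibitors among them, under the rule "The patients will not be permitted to use any of the following medications from Screening till the end of treatment".

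Under SAP 16.3.2, the subgroups of 7.5 feed the number and percentage of patients at BP goal. Separately, three of the four exploratory variables in SAP 16.3.1 compare patients already on ZOF 30 mg or NEB 5 mg with patients switched at Visit 1.

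**The concern.** Screening therapy is the drug taken before the run-in. A switched patient stops that drug at Visit 1, about four weeks before the combination starts, so a search among concomitant medications may look in the wrong place. The class filter is also narrower than the entry criterion. A patient missed on either ground drops out of the subgroup table.

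At stake is whether that table covers the patients it claims to cover, and whether two programmers following the text would produce the same table. A related gap is that the continued-versus-switched contrast in 16.3.1 needs the same Visit 1 information, but the SAP gives no rule for deriving it.

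**Working it through.** The plan states no figure for this point, so the check is to trace the rule.

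**Dates.** By SAP 6.1, an event before the reference date has study day = event date − reference date. With a 4-week run-in, a drug stopped at Visit 1 has day −28. The ±2-day window at Visit 2 makes this −26 to −30. Each value precedes the first combination dose, so SAP 13 labels the drug prior.

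**Choices left open by the text.**
- Source: only records classed as concomitant, or all medication records.
- First dose of study medication: the combination (SAP 6.1, 6.2), or the run-in monotherapy (SAP 14 applies the term to both).
- Recorded stop date of the old drug: the day before Visit 1, or Visit 1 itself.

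**Class assigned by the 7.5 rule.**

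| Drug at screening | Concomitant only; first dose = combination; either stop date | Concomitant only; first dose = monotherapy; stopped the day before | Concomitant only; first dose = monotherapy; stopped at Visit 1 | All records |
|---|---|---|---|---|
| ZOF (own supply recorded as stopped) | none | none | ACE-i | ACE-i |
| Other ACE-i | none | none | ACE-i | ACE-i |
| NEB (own supply recorded as stopped) | none | none | BB | BB |
| Other selective BB | none | none | BB | BB |
| Non-selective BB | none | none | none | none |

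- The last row is empty under every reading.
- The other rows depend on the reading. On the strict one, continuers can be lost as well as switchers, and any non-study ACE inhibitor or beta blocker still found would be a non-permitted medication under Protocol 9.6.
- No cell holds the wrong class; the failure is always a missing class.

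**Size of the certain loss.** The share on non-selective agents is not in the documents. Assuming 5–20%, and using the Protocol 7 cap of 110 patients per run-in drug at Visit 2: 0.05 × 110 = 5.5 (about 6) and 0.20 × 110 = 22.

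**Relation to the run-in subgroup.** By protocol rule, every ACE-inhibitor patient receives ZOF and every beta-blocker patient receives NEB. A correctly derived screening-therapy split therefore gives the same two groups as the run-in split. Derived with losses, it differs only through the missing patients.

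**The case against.** The strongest reply is that the source in 7.5 is a dataset, named in the same way as the medical history data in that paragraph, and not the SAP 13 category. Protocol 9.5, on concomitant therapies, has drugs taken at enrolment recorded in the eCRF, and the flow chart collects concomitant medications at Visit 1. On that reading all ACE-inhibitor and selective beta-blocker patients are found. This is a fair reading and may be the intended one. It does not settle the matter, because the flow chart has a separate row for prior medication and SAP 13 gives concomitant a dated meaning. It also leaves the selective-only filter untouched.

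A second reply is that the ATC sentence was never meant to separate continuers from switchers. That stands: SAP 16.3.1 specifies the contrast on its own, so its absence from the 7.5 list does not mean the analysis was omitted. Only the derivation is missing.

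A third is that listing two equivalent subgroups biases nothing and follows Protocol 14.5.6. That also stands; the overlap is redundancy and not an error.

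A fourth is that the consequences are slight. SAP 16.3.2 specifies only counts and percentages for these subgroups, and SAP 7.5 itself disclaims high power within them. This is right and sets the severity.

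**Conclusion.** The point holds as a low-severity gap in the SAP's wording. What is certain is that non-selective beta-blocker users have no class, although the protocol admits them. The 6–22 patients only illustrate the possible size, because they rest on an assumed share; the true number could be zero. What is conditional is the loss of patients whose drug was replaced at Visit 1, which depends on how the source and the first dose are read.

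A reader might infer that switched patients are misclassified, or that the subgroup would be empty or consist of protocol deviators. The documents do not support either as a general statement. No reading puts a patient in the opposite class. Near-total loss needs the strict date reading and disappears if all medication records are searched.

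The primary and secondary analyses do not use this rule. Nor do the continued-versus-switched variables of 16.3.1, which lack a derivation of their own.

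One further inconsistency bears on that derivation. Protocol 4 says "Patients who were on ZOF or NEB treatment at Screening, will continue to receive the same drugs", without a dose, while Protocol 7 ties continuation to ZOF 30 mg or NEB 5 mg. The documents do not say whether any patients enter on another dose. The two sections must be reconciled before such patients can be assigned to an analysis group.

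**What to change.** Before database lock, change SAP 7.5 and 16.3.1 as follows:

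1. Derive screening therapy from the antihypertensive recorded at Visit 1, whether it is later labelled prior or concomitant.
2. Identify it by the ACE-inhibitor class and all beta-blocker ATC classes.
3. Keep the protocol-listed ACE-i/beta-blocker subgroup, with a note that by design it matches the run-in split.
4. From the same Visit 1 record, derive continued versus switched, use it for the 16.3.1 variables that need it, and show it within run-in drug as a supplement.
5. Reconcile Protocol 4 and 7 on who counts as a continuer, then state the analysis group for patients on another dose.

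Items 1–4 cost a few lines of SAP text and a short derivation. The Visit 1 medication data are already collected. Item 5 is a protocol clarification for the sponsor.
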